This will be a pilot study with an enrollment goal of 20 patients post stroke with a weak or sensory impaired UE. Mayo Clinic Florida received approximately 39 patients with stroke diagnosis per month according to records taken from January through October of 2019. Patients will be evaluated as routine standard part of care where standard chart review will be done and then patients will be screened for study inclusion for appropriateness for

participation in this study using the Brief Interview of Mental Status (BIMS) with scores $>$ or $=$ to 13 indicating intact cognition. If the patient does not score $>$ or $=$ to a 13 they will not be included in this study. If patient consent is obtained the patient will be enrolled in this study. Baseline data will be collected including pain, edema, nail bed color, sensation, skin integrity, grip strength and movement of the hemiparetic UE and photo taken prior to application of the sleeve and upon completion of 2nd check. The NIH score will be recorded as well at baseline. The patient's arm will be checked approximately every 2 hours following, for a total of approximately four hours recording pain, edema, nail bed color, sensation, skin integrity, movement, and patient tolerance during every check. Adverse effects attributable to sleeve usage will warrant removal of the SCD sleeve. These include, but are not limited to, compromised skin integrity, pain, patient intolerance, and increased edema or cyanosis. Subjects to which the SCD sleeve is removed will no longer be included in the study.

Application of LE SCD Sleeve:

Calf size LE SCD sleeve will be placed on the weak or sensory impaired UE below the cubital fossa and may include the hand if necessary. The patient's arm will be placed on a pillow providing support to the shoulder and arm keeping elbow extended. The sleeve will be applied with the standard approach/application to the calf when applied with adequate 2 finger spacing between the SCD sleeve and skin of the UE ². Patients will otherwise be allowed to move their arm as able freely while wearing the SCD sleeve.

Step -by –Step Schedule:

[figure not shown]
1. Order for PT or OT services received, OT and PT evaluations will be completed
2. PT/OT will screen during OT/PT evaluation process and perform standard protocol chart review for potential patient inclusion into this study and order will be obtained for inclusion by MD

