3. MD will place an order in the chart for the SCD and sleeve to be placed on the affected UE
4. Reason for SCD study and risks will be explained; and once all questions by patient are answered satisfactorily, informed consent will be signed by patient
5. Baseline skin and neurovascular assessment performed and documented by PT or OT prior to placement of SCD sleeve on patient (Picture of UE taken pre application and attached to chart):
 - a. Patient tolerance of wearing sleeve
 - b. Pain
 - c. Edema
 - d. Nail bed color
 - e. Skin integrity
 - f. Sensation
 - g. NIH Motor Arm subsection #5 score
 - h. BIMS score
 - i. NIH stroke scale score
 - j. Grip strength measure hand dynamometer
6. Measure circumference of affected forearm using tape measure to determine size of SCD sleeve
7. Placement of SCD sleeve on affected UE below cubital fossa, document patient initial tolerance and start time (T_1).
8. Subsequent UE checks to occur as follows, for a total of approximately four hours wearing time*:
 - 1st check – approximately 2 hours (h) after initial application (i.e. T_1).
 1. Take sleeve off patient, assess arm, obtain data (a.-g.), and document findings.

- 2nd check - approximately 2 hours (h) later (i.e. $T_1 + 2h = T_2$).
 1. Take sleeve off patient, assess arm, obtain data (a.-g.) and document findings (take post picture of UE and attach to chart).

* Any adverse effects, including patient tolerance, attributable to sleeve usage will warrant removal of SCD sleeve

Time (T)	T_i Baseline	T₁ 1st check	T₂ 2nd check
Patient tolerance “Are you tolerating this sleeve (Y/N)?”			
Pain (VAS)			
Edema (Girth)			
Nail bed color			
Skin integrity (Intact/Impaired)			
Sensation (Intact/Impaired)			
Motor Arm subsection of NIH			
Hand Dynamometer			
BIMS score			
NIH stroke scale score			

Subject Remuneration:

Subjects will not be provided a monetary incentive.

Sample Size:

The sample size of this pilot study will be 20 subjects. The average number of subjects when testing the use or effectiveness of a device is commonly between 10-40 subjects. This study is within the average range for this type of study.

Data Collection May Include:

1. Age
2. Gender
3. Race
4. Diagnosis
 - a. type of stroke
 - b. location of stroke
5. Vitals (reviewed and considered for inclusion criteria, not included in data collection chart)

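### Both checks take the sleeve off before tolerance and pain are recorded, and the removal rule, read literally, drops the patients who did not tolerate it

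*Protocol*

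**What the plan says.** All of the following is in the protocol.

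- **Step-by-Step Schedule, item 5:** "Baseline skin and neurovascular assessment performed and documented by PT or OT prior to placement of SCD sleeve on patient". The list that follows starts with (a) "Patient tolerance of wearing sleeve" and (b) pain.
- **Item 7:** the sleeve is placed and staff "document patient initial tolerance and start time".
- **Item 8, 1st check (about 2 hours):** "Take sleeve off patient, assess arm, obtain data (a.-g.), and document findings".
- **Item 8, 2nd check (about 2 hours later):** "Take sleeve off patient, assess arm, obtain data (a.-g.) and document findings (take post picture of UE and attach to chart".
- **Data table:** the tolerance question is "Are you tolerating this sleeve (Y/N", with columns for baseline and both checks.
- **Starred note under the schedule:** "Any adverse effects, including patient tolerance, attributable to sleeve usage will warrant removal of SCD sleeve".
- **Study Design or Overview:** the arm is checked about every 2 hours, "recording pain, edema, nail bed color, sensation, skin integrity, movement, and patient tolerance during every check". The same paragraph says that patients whose sleeve is removed are no longer part of the study.
- **Background:** tolerance is to be assessed over about 4 hours in one day.
- **Endpoints, Primary:** the sleeve is to be usable and tolerable to the patient 100% of the time.

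**The concern.** The study asks whether patients can tolerate a calf sleeve, cycling at a fixed pressure of about 45 mmHg, on a weak or sensory-impaired arm. Discomfort that comes with compression can ease once the sleeve is off. A present-tense question and a pain scale with no stated recall period, both used on a bare arm, may miss some of it. The likely error is towards a favourable answer on the primary endpoint. With 20 patients and a 100% criterion, one changed answer decides whether the criterion is met.

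A second issue sits beside the first. Asking under compression makes an honest No more likely to be heard. But a No warrants removal, and removal ends inclusion. If that means leaving the analysis, the answers that matter most disappear from the result.

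**Working it through.** **Order of procedures.** The plan gives no figure for this point, so the check is a reading of when each scheduled entry is taken.

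| Step | Sleeve at time of entry | Tolerance (a) | Pain (b) |
|---|---|---|---|
| Item 5, baseline | not yet placed | listed | yes |
| Item 7, placement | on, zero wear | yes (initial) | no |
| Item 8, 1st check | just removed | yes | yes |
| Item 8, 2nd check | just removed | yes | yes |

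Per patient, this gives one scheduled on-sleeve tolerance entry, at zero wear, and no on-sleeve pain score. Over the trial, the post-wear entries number at most 20 × 2 = 40 for tolerance and 40 for pain, and all of them follow removal. Forty is a maximum, because a patient whose sleeve comes off early does not complete both checks. The overview paragraph says that pain and tolerance are recorded at each check but gives no different order.

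**What one answer is worth.** Each patient is 1/20 = 5 percentage points. 20/20 has an exact two-sided 95% lower limit of 0.025^(1/20) = 83.2%. 19/20 = 95% has limits of 75.1% and 99.9%.

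**Size of the order effect.** This cannot be computed. It needs the rate of intolerance under compression, the share of those patients who speak up between checks, and the share of the rest who answer Yes once the sleeve is off. The protocol gives none of these.

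**Removal rule, a separate effect.** Let r be the number of sleeve-related removals among 20 placed. If they are dropped, the result is (20 − r)/(20 − r) = 100% for every r below 20, provided the rest answer Yes. If they are counted as not tolerated, it is (20 − r)/20. The limits are Clopper-Pearson: the 2.5% quantile of Beta(x, n − x + 1) and the 97.5% quantile of Beta(x + 1, n − x), with x = 20 − r and n = 20.

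| r | Dropped | Counted as not tolerated | Exact 95% CI when counted |
|---|---|---|---|
| 1 | 19/19 = 100% | 19/20 = 95% | 75.1% to 99.9% |
| 2 | 18/18 = 100% | 18/20 = 90% | 68.3% to 98.8% |
| 3 | 17/17 = 100% | 17/20 = 85% | 62.1% to 96.8% |

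These figures are the same whether the question is asked before or after removal. They measure the counting rule and say nothing about the order effect.

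**The case against.** The case for leaving item 8 alone has real weight.

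- **The line may just be compressed.** It covers seven items, most of which need a bare arm, and the present-tense question fits being asked with the sleeve on. Staff may well do that. The protocol does not tell them to, however, and its only stated order is removal first.
- **Little may be lost.** Item (a) concerns wearing the sleeve, and it is asked at the moment of removal. Patients must score 13 or more on the BIMS, and those who cannot report pain consistently are excluded. Intolerance at any time leads to removal, so reaching 4 hours is itself some evidence of tolerance. This stands and keeps the point modest. It is not a full answer: the Background puts spatial neglect at 30% or more of stroke survivors, neglect is not an exclusion, and waiting for patients to volunteer discomfort is weaker than asking them.
- **Off-sleeve pain matches the off-sleeve baseline.** This stands, and that score should be kept.
- **Item 5a.** A reader might infer that the baseline tolerance value is meaningless because no sleeve has been placed. Item 7 supplies the first value, and the overview's baseline list omits tolerance, so the entry is a clerical slip.
- **No longer included may mean only that participation ends.** Analysis sets are commonly left to a statistical analysis plan, which is not at hand. That reading is possible. But the sentence is in the protocol, and its literal reading makes a 100% result self-fulfilling, so it needs clarifying there.

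**Conclusion.** The point holds in a limited form. As written, no tolerance answer or pain score is scheduled under compression after zero wear time, although tolerance is the primary endpoint. The likely direction of any error is towards tolerated; that is a judgement about discomfort easing on removal, and the protocol gives no data on it. The size is unknown and probably modest.

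A reader might infer that on-sleeve discomfort goes unrecorded altogether, or that the tolerance result would be invalid. The documents do not support that, because recall at the check and the removal rule both capture some of it. Nor should the gap between 18/18 and 18/20 be read as the bias from question order. It belongs to the removal rule alone, and only if that rule takes patients out of the denominator. On that reading it is the larger and more certain problem: 100% against 90% (68% to 99%) with two removals.

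**What to change.** 1. Reword item 8 at both checks: with the sleeve on and the pump running, ask (a) and score (b); then remove the sleeve, repeat the pain score, and obtain (c) to (g). Removal for (c) to (g) is sound and stays.
2. Strike tolerance from the pre-placement list in item 5 and use the item 7 entry as the first tolerance value.
3. State that the primary result uses the on-sleeve answers, with every patient in whom the sleeve was placed in the denominator. Any removal for intolerance, pain or another sleeve-related adverse effect, at or between checks, counts as not tolerated. Amend the overview sentence to say that such patients stop wearing the sleeve but stay in the analysis.

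The cost is one reworded line per check, one deleted baseline entry, one extra pain score per check (2 per patient, at most 40 in all), and the wording on how removals count. No visits, equipment or patients are added.

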Adults post stroke admitted to MCJ, with a weak upper extremity, or diminished sensation, which provide consent of participation by self-agreement. Patients with a weak or sensory impaired UE will be determined using the NIH Motor Arm subsection from the NIH scale and score a 1-4, dynamometry for hand grip strength or sensation deficits using the AISA C2-T2 standard points. Patients who have received thrombolytic therapeutic medicine > 13 hours (per site specific policy) will not be excluded from inclusion in this study. Patients who score > or = to 13 on the BIMS to ensure intact cognition.

Exclusion Criteria:

Inability to provide consent of participation; subjects with aphasia or the inability to effectively communicate their pain consistently or with questionable cognitive reliability scoring <13 on the BIMS (will be excluded), has an existing invasive line (PICC line, central venous catheter, AV fistula or AV graft); recent surgery or vein ligation in the involved extremity; recent skin graft in the involved extremity; confirmed DVT in the affected, upper extremity including axillary or subclavian veins; open or active wounds or infection in the involved extremity; upper extremity ischemia, gangrene, cellulitis or severe arteriosclerosis in the affected upper extremity; status-post axillary lymph node dissection on the involved side; congestive heart failure (CHF) acute exacerbation; acute edema of unknown etiology in the involved upper extremity; subjects with extreme deformity of the affected upper extremity; subjects with an acute kidney injury; subjects who are hemodynamically unstable^{1,7,17}; subjects under age 18 and over age 100; and patients who have received thrombolytic therapeutic medicine administered <13 hours (per site specific policy) prior to application of SCD sleeve. Women confirmed pregnant at the time of admission will be excluded.

Biospecimens

Collection of blood samples. When multiple groups are involved copy and paste the appropriate section below for example repeat section b when drawing blood from children and adults with cancer.

- a. **From healthy, non-pregnant, adult subjects who weigh at least 110 pounds.** For a minimal risk application, the amount of blood drawn from these subjects may not exceed 550ml in an 8-week period and collection may not occur more frequently than 2 times per week.

Volume per blood draw: _____ ml

Frequency of blood draw (e.g. single draw, time(s) per week, per year, etc.) _____

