- b. **From other adults and children considering age, weight, and health of subject.** For a minimal risk application, the amount of blood drawn from these subjects may not exceed the lesser of 50 ml or 3 ml per kg in an 8-week period, and collection may not occur more frequently than 2 times per week.

Volume per blood draw: _____ ml

Frequency of blood draw (e.g. single draw, time(s) per week, per year, etc.) _____

Prospective collection of biological specimens other than blood: _____

Review of medical records, images, specimens

Check all that apply (data includes medical records, images, specimens).

Only data that exists before the IRB submission date will be collected.

Date Range for Specimens and/or Review of Medical Records:

Examples: *01/01/1999 through 12/31/2015*, or all records through *mm/dd/yyyy*.

Note: The Date Range must include the period for collection of baseline data, as well as follow-up data, if applicable.

The study involves data that exist at the time of IRB submission **and** data that will be generated after IRB submission. Include this activity in the Methods section.

Examples

- The study plans to conduct a retrospective chart review and ask subjects to complete a questionnaire.
- The study plans to include subjects previously diagnosed with a specific disease and add newly diagnosed subjects in the future.

The study will use data that have been collected under another IRB protocol. Include in the Methods section and enter the IRB number from which the research material will be obtained. *When appropriate, note when subjects have provided consent for future use of their data and/or specimens as described in this protocol.*

Enter one IRB number per line, add more lines as needed

Data Specimens Data & Specimens _____

Data Specimens Data & Specimens _____

Data Specimens Data & Specimens _____

Data Analysis

Power Statement:

The primary aim is use and tolerability which in twenty subjects should be adequately powered to eighty percent.

Data Analysis Plan:

The data will be largely descriptive around the aims in terms of age, gender, type of stroke, NIH stroke scale severity, weak upper extremity and other laboratory data from the electronic medical record retrospectively.

Endpoints:

Primary:

To establish that a leg sleeve and SCD can be used on a weak or sensory impaired UE post stroke and is tolerable to the patient 100% of the time.

Secondary:

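### Primary tolerability has no per-patient definition, so objective harm first seen at the final check, or harm that ends wear earlier, need not count as a failure

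*Protocol*

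**What the plan says.** **Primary endpoint (Endpoints, Primary).** It has two parts: that the leg sleeve and pump can be used on the affected arm, and that this "is tolerable to the patient 100% of the time". Neither part is defined for a single patient.

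**Tolerance measure (Step-by-Step Schedule, data table).** The one row labelled patient tolerance asks "Are you tolerating this sleeve (Y/N". Pain, edema, nail bed color, skin integrity and sensation are separate rows, recorded at baseline and at both checks. No sentence ties them to the primary endpoint.

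**Adverse effects (Study Design or Overview).** Effects attributable to the sleeve lead to its removal: "These include, but are not limited to, compromised skin integrity, pain, patient intolerance, and increased edema or cyanosis". The same paragraph says that a subject whose sleeve is removed leaves the study. It does not say that such a subject counts as a failure.

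**Timing (Step-by-Step Schedule).** The arm is examined about 2 hours after application and about 2 hours after that. The sleeve is taken off at each check; the second ends the wearing period.

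**Population (Study Design or Overview; Inclusion Criteria).** There is an "enrollment goal of 20 patients post stroke with a weak or sensory impaired UE". Eligible patients are "Adults post stroke admitted to MCJ, with a weak upper extremity, or diminished sensation". They qualify by a Motor Arm score of 1-4, or by "dynamometry for hand grip strength or sensation deficits using the AISA C2-T2 standard points".

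**The concern.** Self-report is a weak detector of harm in an arm with reduced feeling. Such a patient may answer yes while the skin is damaged or the nail beds are discolored. The protocol's safeguards on self-report are the BIMS threshold and the exclusion of patients who cannot communicate pain consistently (Strengths; Exclusion Criteria). They cover cognition and communication, not sensation.

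Objective findings could compensate, but they are given a role only through removal. That leaves the same sign handled in two ways, neither of which counts it as a failure:

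- Seen at the first check, it leads to removal, and the patient is no longer in the study.
- Seen at the second check, it changes nothing, because every sleeve comes off then. With a yes answer, the patient can be counted as tolerating the sleeve.

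Both gaps push the result towards 100%. The Background makes later work on benefit depend on this study first showing that the sleeve can be used on the arm, so a favorable figure would carry weight.

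**Working it through.** **1. The plan's own figure.** The Power Statement claims 80% power with 20 subjects. It gives no null rate, alternative rate, alpha or sidedness, so the figure cannot be reproduced, only back-solved. If success means 20 of 20, then power = p^20, and 80% power needs p = 0.80^(1/20) = 0.989. At a true per-patient tolerability of 0.95, the chance of 20 of 20 is 0.95^20 = 0.358. A 100% criterion is therefore very sensitive to how each patient is coded.

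**2. One sign first seen at the second check, with a yes answer.** Inputs: n = 20 (Sample Size) and the 100% criterion (Endpoints). Clopper-Pearson 95% limits:

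- Counted as tolerated, 20/20 = 100%. Lower limit = 0.025^(1/20) = 0.832. CI 83.2-100%.
- Counted as a failure, 19/20 = 95%. Lower limit = 2.5% point of Beta(19, 2) = 0.751; upper limit = 0.975^(1/20) = 0.999. CI 75.1-99.9%.

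One coding decision that the protocol does not settle determines whether the criterion is met.

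**3. One removal at the first check, with the other 19 tolerating.**

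- Dropped from the denominator, 19/19 = 100%. Lower limit = 0.025^(1/19) = 0.824.
- Kept as a failure, 19/20 = 95%, with the interval in step 2.

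**4. How likely is at least one patient of the step 2 kind?** Let q be the probability, averaged over all enrolled patients, that an objective sign is first seen at the second check and the answer is still yes. The protocol gives no value, so q is assumed. The chance of at least one in 20 is 1 - (1 - q)^20:

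| Assumed q | (1 - q)^20 | Chance of at least one |
|---|---|---|
| 1% | 0.818 | 18% |
| 2% | 0.668 | 33% |
| 5% | 0.358 | 64% |
| 10% | 0.122 | 88% |

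**The case against.** **The endpoint is never equated with the yes/no item.** This stands. A reader might infer that the yes/no answer is the primary endpoint and that objective signs are shut out. The protocol does not say so, and the part about whether the sleeve can be used may be meant to take them in. What remains is that nothing says whether or how they enter, so the choice could be made after the data are seen.

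**Not all patients have impaired sensation.** This stands. A reader might infer that the sample is enrolled for sensory loss. Entry is by weakness or sensory impairment, and the share with sensory impairment is unknown. The weakness of self-report applies most to that subset.

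**Harm at the second check would not be hidden.** This also stands. The arm is examined, skin changes are described by type and area, and a photograph is taken. The signs would be available beside any tolerance figure; the gap is that they need not alter it.

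**Keeping perceived tolerance apart from objective safety is legitimate, and the SAP may define the derivation.** Reporting the two separately is a fair choice, and derivation detail often sits in an SAP, which is not at hand. But the 100% criterion and the sentence taking removed subjects out of the study are both in the protocol. Read together, they allow harm at the first check to leave the denominator and harm at the second to count as tolerated.

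**Conclusion.** The point holds in this form. The protocol sets a 100% tolerability criterion without a per-patient definition, offers a yes/no self-report as its only tolerance measure, and gives objective harm a role only through a removal rule that cannot register a sign first seen at the second check. The removal sentence may also take earlier failures out of the denominator. With n = 20, one such patient separates 20/20 from 19/20, with lower 95% limits of 83.2% and 75.1%.

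The probabilities from 18% to 88% rest wholly on assumed rates of 1% to 10%; the protocol supports no particular rate, and a claim that such an event is likely would go too far. Nor is it certain that removed patients are excluded from analysis: the sentence could mean only that participation ends. The defect is that the text permits the favorable reading in both places. It should be corrected, but the study does not need redesign.

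**What to change.** **Endpoint.** In the Endpoints section, define the primary outcome per patient, among all patients in whom the sleeve was applied. Success requires all three of the following; anything else is a failure:

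- about four hours of wear completed;
- a yes answer at both checks;
- none of the sleeve-attributable adverse effects already listed in Study Design or Overview ("compromised skin integrity, pain, patient intolerance, and increased edema or cyanosis") recorded at either check, including those first seen at the second.

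**Denominator.** Amend the sentence in Study Design or Overview so that subjects whose sleeve is removed stay in the analysis as failures. The removal rule itself is not changed.

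**Reporting.** Give the yes/no answer alone as a supporting measure, and show both results by baseline sensation (intact or impaired).

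**Cost.** The signs are already recorded at baseline and both checks, so no visit or examination is added. This is still more than one derived variable. The chart records a start time but has no stop time and no field for attribution to the sleeve; both must be added. The protocol must state what counts as an increase in edema or pain beyond measurement variation, and whether redness alone, which Data Collection lists under skin integrity, makes a patient a failure. The reported success proportion may be lower than from self-report alone.

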6. Medical History (including a family history of thrombosis, coagulopathy, blood clots, or clotting disorders) (reviewed and considered for inclusion criteria, not included in data collection chart)
7. Affected UE pain using Visual Analog Scale (VAS) 1-10 Pain Scale
8. Affected UE nail bed color (normal, cold, dusky or bluish)
9. Affected UE strength using Motor Arm Subscale # 5 of the NIH stroke scale
10. Affected UE sensation using cotton swab and dermatome points (C2-T2) documenting Intact or Impaired
11. Affected UE edema using arm circumference measurement proximal to wrist crease and 5 inches distal to cubital fossa and for size of sleeve needed using tape measure in inches as follows:

Medium	<21 inches
Large	<26 inches
12. Affected UE skin integrity documenting Intact or Impaired (describing redness, rash or bruising and area of arm if present)
13. BIMS score
14. Most recent NIH stroke scale score documented in chart prior to application of sleeve
15. Grip strength measured via hand grip dynamometer.

Data Handling:

Data will be entered into Redcap data collection system.

Feasibility and Time Frame:

From January through October 2019 Mayo Clinic Florida averaged 39 patients with a stroke diagnosis per month with varying degrees of immobility in their affected UE. Due to the high number of stroke patients with UE weakness, decreased sensation and/or immobility, we feel this study has good general feasibility at attaining enrollment in a reasonable timeframe. We anticipate completing this study in 1-3 months, enrolling 4-5 eligible persons to be studied per week for a total of 20 subjects acquired in a 1-3-month time frame. Feasibility is good for this project.

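### The nail bed colour item mixes a temperature term with colours and has no level for pale, so some circulatory findings have no single fitting code

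*Protocol*

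**What the plan says.** Item 8 under Data Collection May Include reads "Affected UE nail bed color (normal, cold, dusky or bluish"). This is the only place in the protocol that gives levels for the item.

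Nail bed colour is entry d of step 5 in the step-by-step schedule, which is headed "Baseline skin and neurovascular assessment performed and documented by PT or OT prior to placement of SCD sleeve on patient". It is repeated at both checks. For the 1st check, step 8 says "Take sleeve off patient, assess arm, obtain data (a.-g.), and document findings", and the instruction for the 2nd check is the same apart from the added photograph. The recording table has one nail bed row for baseline (Ti), T1 and T2 and prints no levels in it, although the skin integrity and sensation rows do print theirs.

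Three other provisions bear on the point:

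- **Skin.** Item 12 of the list is "Affected UE skin integrity documenting Intact or Impaired (describing redness, rash or bruising and area of arm if present").
- **Photographs.** One is taken before application ("Picture of UE taken pre application and attached to chart") and one at the 2nd check ("take post picture of UE and attach to chart").
- **Removal.** Study Design or Overview introduces the adverse effects that warrant taking the sleeve off with "These include, but are not limited to, compromised skin integrity, pain, patient intolerance, and increased edema or cyanosis".

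**The concern.** A categorical item works when its levels describe one attribute and cover the findings it is meant to catch. These four levels describe two attributes, colour and temperature, and leave out one colour.

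This matters more here than it would for a minor form field. The Limitations section says that the leg sleeve is not meant for the arm and that the pump pressure is fixed, and it relies on regular monitoring. The Background says that safety evidence in the immobile arm is scarce. The exclusion criteria show that arterial supply was considered at entry, since limb ischaemia and severe arterial disease are excluded. Patients may also qualify through reduced sensation, which makes their own report of pain a weaker warning and an assessor-read sign more useful.

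The analysis is planned as mostly descriptive, so the recorded categories would themselves be the reported result. An attribute that is not recorded at the bedside cannot be recovered later by a statistical analysis plan.

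**Working it through.** The protocol states no figure to reproduce, and the point depends on no power, alpha or event count. The check is to set the levels of item 8 against the findings an assessor could meet, and then to look for another field that would hold what is lost.

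**Step 1. Findings against levels.**

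| Finding | Levels of item 8 that fit | Result |
|---|---|---|
| Warm, normal colour | normal | Codable |
| Warm, dusky or bluish | dusky, bluish | Codable |
| Warm, pale | none | No fitting code |
| Cold, pale | cold | Temperature recorded, pallor not |
| Cold, normal colour | cold and normal | Two codes apply |
| Cold, dusky or bluish | cold and a colour | Two codes apply |

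The protocol does not say whether an assessor may enter more than one level. If only one is entered, the last two rows lose an attribute, and assessors may differ in which one they keep.

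**Step 2. Change over Ti, T1 and T2.**

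- A hand that is cold at baseline and then turns dusky or bluish can be given a different code, so that change is visible.
- A hand that is cold with normal colour at baseline and cold and pale later is cold both times, so the change is not visible.
- A hand that stays cold with normal colour could be coded normal at one assessment and cold at the next, which shows a change that did not occur.

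**Step 3. Other fields.**

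| Field | Pallor? | Temperature? |
|---|---|---|
| Skin integrity (intact/impaired; prompts for redness, rash, bruising) | Not prompted | No |
| Sensation (cotton swab, intact/impaired) | No | No |
| Girth | No; bears on swelling | No |
| Photographs | Possibly, before application and at the 2nd check | No |

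No field records capillary refill. Girth does bear on venous congestion, so nail bed colour is not the only circulatory sign. It is the only coded sign of colour or perfusion.

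**Step 4. Readings on this scale.** 20 subjects × 3 assessments = 60 readings at most, of which 20 × 2 = 40 come after application. These are upper limits on the use of the scale, not counts of affected readings. The protocol gives no rate of pale nail beds or of cold paretic hands, so no such count can be derived.

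**The case against.** The strongest reply is that this is a loosely worded label, with few consequences that the text can prove.

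- **The levels may not be closed.** They stand in parentheses in a list of data that may be collected, the recording table leaves the row blank, and the REDCap form is not shown. Nothing forbids writing pale, or cold together with a colour. This stands. A reader might infer that a pale nail bed must be recorded as normal, but the protocol does not say so. What remains is that the only levels stated do not include it.
- **A cold hand can be coded.** True. A cold hand of normal colour is ambiguously coded, not necessarily miscoded.
- **Baseline is recorded.** True. A reader might infer that change from baseline cannot be interpreted at all. Step 2 shows that only certain combinations are lost.
- **The sleeve is off when the nail bed is read.** True at both checks. The scale therefore describes the hand after about two hours of wear, not during a compression cycle. The protocol offers no support for calling pallor an expected finding, and the exclusion of patients with ischaemia or severe arterial disease of the limb makes it less likely.
- **Safety is covered elsewhere.** In part. The removal list is open-ended, and the one colour sign it names, cyanosis, is covered by dusky and bluish. An assessor remains free to notice pallor and act on it, so the protocol does not support a claim that pallor would be ignored. The gap is in what is recorded. The photographs help with colour, but not at the 1st check and not with temperature.
- **No endpoint uses the item.** Correct. The primary endpoint concerns use and tolerability, and tolerance is asked as yes or no.

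These replies limit the point to data quality. They do not supply a pale level or separate temperature from colour.

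**Conclusion.** The point holds as a modest measurement flaw. The stated levels of item 8 mix two attributes and omit pale, and no other coded field fills the gap. A pale nail bed has no fitting code, and a cold hand fits cold as well as its colour.

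The effect is confined to the descriptive safety data. The yes/no tolerance answer and the sample size of 20 are untouched.

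The conclusion assumes that the data form uses the levels as item 8 lists them. If the form already allows pale, or several entries at once, the practical loss shrinks or disappears, and the protocol text should be brought into line with the form.

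**What to change.** Replace item 8 with two entries, each recorded at Ti, T1 and T2:

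1. Nail bed colour: normal / pale / dusky / bluish.
2. Hand temperature: normal / cold.

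Print these levels in the recording table, as is already done for skin integrity and sensation, and describe each entry as change from the patient's own baseline. Keep dusky and bluish separate, since the protocol distinguishes them. No composite count of vascular changes is needed.

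The cost is one extra brief entry at each assessment already scheduled and a small edit to the data form. No removal or stopping rule changes.
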